#### **Primary outcome:**

- **Speed/range of motions of the knee.**

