### Knee Function Assessment

#### 1. Speed of motion

The 10-meter timed walking test is a well-established and documented test for assessment for gait speed in patients. However, due to space limitations and the exhaustive nature of the test for patients with OA, the **6-meter test timed walking gait test** has been documented to be a valid and reliable substitute. Patients will be asked to walk a straight line of 6 meters where the time taken to complete the distance will be measured. (<7.5 seconds is normal).

The **Time up and go test (TUG)** is to determine fall risk and measure the progress of balance, sit to stand and walking. Patients will be asked to stand up from a chair, walk as quickly as possible in their a safe and most comfortable gait until they pass to 3 meters (10 feet) end of marked course with both feet. Turn around and walk back to the chair, time will be counted to the moment until the back of patients touches the back of the chair. ( $\leq 10$  seconds = normal;  $\leq 20$  seconds = good mobility, can go out alone, mobile without gait aid;  $\leq 30$  seconds = problems, cannot go outside alone, requires gait aid;  $\geq 14$  seconds indicates high risk of falls)

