#### 2. Range of motion

The **active range of motion test** predicts the mobility of the joint by measuring the amount of active knee extension and flexion. "For measurement using the goniometer, 1 arm of the goniometer is placed parallel to the shaft of the femur lining up with the greater trochanter, and the other arm is placed parallel to the shaft of the lower leg lining up with the lateral malleolus of the fibula. The axis of the goniometer is placed over the lateral femoral epicondyle. Knee extension: The patient is supine. The heel of the limb of interest is propped on a bolster, assuring the back of the knee and calf are not touching the support surface. The patient is asked to actively contract the quadriceps. The amount of knee extension is recorded with the goniometer. Knee flexion: The patient is prone. The patient flexes the knee as far as possible. The amount of knee flexion is recorded with the goniometer."(15)

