#### **Data Processing and Statistical Analysis:**

Demographic characteristics will be demonstrated using Student t-test or Chi-square test for continuous data and categorical data respectively where appropriate. The accuracy of primary measurements between the treatment (proprioceptive knee brace + routine post-operative procedures) and control (routine post-operative procedures) groups at the 4 time points (Pre-operative, 6 weeks, 6 months, 12 months) will be compared using ANOVA. Secondary outcomes and different types of patient-oriented quality of life questionnaires collected at the 4 time points will be compared using ANOVA likewise. All statistical analysis will be carried out using IBM SPSS version 25 (Armonk, NY:IBM Corp).

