#### **Secondary outcome:**

- **Patient's clinical outcome (knee stability and function), HRQoL and satisfaction.**  

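### The primary outcome covers two to four measures with no lead measure or deciding visit named, while the sample size uses one 0.05 alpha tied to none of them

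*Protocol*

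**What the plan says.** The whole definition in the Protocol, section *Primary outcome*, is "Speed/range of motions of the knee".

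The content has to be read from the assessment section, whose sub-headings match those words:

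- *1. Speed of motion* holds two timed tests. For the walk: "Patients will be asked to walk a straight line of 6 meters where the time taken to complete the distance will be measured". The second, TUG, "is to determine fall risk and measure the progress of balance, sit to stand and walking".
- *2. Range of motion* holds one test with two recorded values. It "predicts the mobility of the joint by measuring the amount of active knee extension and flexion", and extension and flexion are each read from the goniometer in a different position.

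The assessment schedule lists the 6-metre gait test, TUG and active range of motion as three rows, each ticked at all four visits.

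*Data Processing and Statistical Analysis* refers to "The accuracy of primary measurements between the treatment" and control groups, and says that these "at the 4 time points (Pre-operative, 6 weeks, 6 months, 12 months) will be compared using ANOVA". Three of those time points are post-operative.

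*Sample Size Estimation* (section F) gives an effect size of 0.5, 95% power, an alpha of 0.05, 12 participants per arm, and 15 per arm after a 25% allowance for attrition. It links these figures to yearly case numbers at the hospital and not to a measure or a visit.

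**The concern.** A primary outcome should tell a reader, before the data are seen, which single result decides the trial. Here a slash joins two constructs, the tests beneath them number three or four, and there are three post-operative visits with none marked as decisive. An investigator who reported whichever speed or range measure, at whichever visit, looked best would not be departing from the protocol.

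Two things are at stake. One is interpretation: a favourable result on a measure and visit that were not named in advance cannot be read as confirmatory. The other is the error rate: one alpha of 0.05 is planned, but several measures may draw on it.

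**Working it through.** **Step 1. Count the candidate primary measures.**

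| Reading of the primary outcome | Items | K |
|---|---|---|
| Constructs | speed; range | 2 |
| Scheduled tests | 6-metre walk; TUG; active range of motion | 3 |
| Recorded values | 6-metre walk; TUG; active extension; active flexion | 4 |

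No section of the protocol chooses among these or picks one of the three post-operative visits.

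**Step 2. See whether the sample size reveals the intended measure.** The attrition step reproduces: 12 × 1.25 = 15 per arm, 30 in total. The 12 itself cannot be traced to a measure or visit, because 0.5 is given without an outcome and without saying whether it is Cohen's d or f. For a single two-sided t test with 12 per arm (22 degrees of freedom, noncentrality d × √(12/2)):

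- 0.5 read as d: noncentrality 0.5 × 2.449 = 1.22, power about 22%.
- 0.5 read as f: for two equal groups d = 2f = 1.0, noncentrality 2.45, power about 65%.

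Neither is the stated 95%. A repeated-measures calculation can give other values, depending on unstated settings. So the sample-size text does not identify the primary measure.

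**Step 3. False-positive chance if any one measure may count.** Assumptions, none of them stated in the protocol: the brace has no effect; each measure gets one two-sided test at 0.05; success on any one counts; nothing is adjusted.

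Independent measures, 1 − 0.95^K:

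- K = 2: 1 − 0.9025 = 9.75%
- K = 3: 1 − 0.8574 = 14.3%
- K = 4: 1 − 0.8145 = 18.5%

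Equally correlated measures (correlation r, normal test statistics), by numerical integration over the shared component u:

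1 − ∫ φ(u) [Φ((1.96 − √r·u)/√(1 − r)) − Φ((−1.96 − √r·u)/√(1 − r))]^K du

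| r (assumed) | K = 2 | K = 3 | K = 4 |
|---|---|---|---|
| 0.5 | 9.1% | 12.5% | 15.6% |
| 0.7 | 8.3% | 10.9% | 13.0% |

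Simulated t tests with 12 per arm agree: 9.3%, 12.7% and 15.7% at r = 0.5; 8.5%, 11.1% and 13.4% at r = 0.7. Holm's procedure on the same trials gives 3.8% to 4.7%, within 5%.

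**Step 4. Price of keeping several measures primary under Holm.** Simulated t tests, 12 per arm, r = 0.5, all measures equally affected; power per measure:

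| Standardised difference | One unadjusted test | Holm, K = 2 | K = 3 | K = 4 |
|---|---|---|---|---|
| d = 1.0 (f = 0.5) | 65% | 59% | 54% | 50% |
| d = 0.5 | 22% | 16% | 12% | 10% |

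**The case against.** The strongest reply is that the SAP is not shown and may settle much of this. That stands for two items. The choice of ANOVA term (group effect or group-by-time) is commonly left to a SAP, and so is a multiplicity adjustment; neither is claimed as a gap here. It does not stand for the identity of the primary outcome and its deciding visit. The protocol takes on that definition itself and words it too loosely.

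A second reply is that the error rates rest on stacked assumptions. This is fair. The protocol gives no success rule and no correlations, so the percentages show what the wording permits and do not predict what the trial will do.

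A reader might also infer two stronger points that the document does not support.

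- *That TUG could be moved freely between primary and secondary*, because it falls under "Knee Function Assessment" while the secondary outcome is the patient's "clinical outcome (knee stability and function), HRQoL and satisfaction". That heading covers speed, range, KT-1000 and strength alike, so the same argument would make every primary measure secondary. TUG sits under the speed sub-heading, which matches the primary outcome, and is naturally primary. The secondary wording has its own referents in the knee stability test, the strength test and the Knee Society Function Score.
- *That the inflation should be multiplied over visits.* The analysis text reads more naturally as one ANOVA across the four time points than as a separate test at each visit, so no such figure is used.

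**Conclusion.** The point holds. The primary outcome covers two, three or four measures according to how it is read, and the protocol names neither a lead measure nor a deciding visit. Its single alpha of 0.05 is attached to none of them. Confidence in this is high, because it rests on the text alone.

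The size is less certain. If any one success counts and nothing is adjusted, the false-positive chance is about 8% to 16% for two to four measures at correlations of 0.5 to 0.7, and 9.75% to 18.5% under independence, against 5%. If the SAP adjusts, or requires success on all measures, that inflation disappears. An adjustment alone would still not say which measure and visit carry the headline. The trial can be run as designed, but this should be corrected.

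**What to change.** Before any outcome is compared by group:

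1. In *Primary outcome*, name one measure and one deciding post-operative visit. Which ones is the investigators' choice. A suitable analysis is the baseline-adjusted group difference at that visit, using the pre-operative value already collected.
2. In *Secondary outcome*, list the other speed and range measures by name.
3. In *Sample Size Estimation*, state which measure and visit the effect size, alpha and power refer to, and restate the power that 12 per arm gives for that test. This corrects the statement; it is not a request to enrol more.
4. If several measures must stay primary, list them by name and test one contrast each by Holm's procedure at a total two-sided 0.05.

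The model term can be left to the SAP.

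Cost: wording changes in these sections and in the analysis section, with no new data. The measures not chosen lose primary status. The restated power may be less favourable than 95%. Taking the Holm route also costs power on each measure, by the amounts in Step 4 of the working.

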#### **Secondary outcome:**

- **Patient's clinical outcome (knee stability and function), HRQoL and satisfaction.**  
**Complications and adverse events.**

This study is stated in compliance with Declaration of Helsinki and ICH-GCP.

